12.3 Sample Size/Accrual Rate

This trial would be conducted at two institutions to accrue up to 45 patients across all cohorts: 30 for Cohort A, and up to 15 for Cohort B. We have a Precision Cancer Study (Ohio State) that evaluates a pool of 400 patients per year with metastatic cancer through research tumor biopsies and comprehensive clinical tumor sequencing. From this pool, we would enrich patients with *FGFR* alterations. We expect to see actionable *FGFR* alterations in approximately 5% of 400 patients screened a year (200 this year) with advanced solid tumors with any histology. Similar precision trial is in place at University of Michigan (MI-ONCOSEQ), screening 400 patients a year. By combining screening from OSU and UM, we expect to see approximately 40 patients enrolled per year (5% of 800 screened). Quarterly review of accrual at each site would be carried out to identify the number of patients enrolled for therapy. Accrual should be complete in 12 to 18 months.

12.4 Analysis of Secondary Objectives

- Frequency and severity of adverse events and tolerability of the regimen will be collected and summarized by descriptive statistics. As per NCI CTCAE v4.0, the term toxicity is defined as adverse events that are classified as either possibly, probably, or definitely related to study treatment. The maximum grade for each type of toxicity will be recorded for each patient, and frequency tables will be reviewed to determine toxicity patterns for each of the cohorts as well as across cohorts. In addition, we will review all adverse event data that is graded as 3, 4, or 5 and classified as either “unrelated” or “unlikely to be related” to study treatment in the event of an actual relationship developing. The incidence of severe (grade 3+) adverse events or toxicities will be described. We will also assess tolerability of the regimen through

assessing the number of patients who required dose modifications and/or dose delays. In addition, we will capture the proportion of patients who go off treatment due to adverse reactions or even those who refuse further treatment for lesser toxicities that inhibit their willingness to continue participation on the trial. All patients who have received at least one dose of any of the therapeutic agent will be evaluable for toxicity and tolerability.

- Overall and Progression Free Survival as time-to-event outcomes. Kaplan-Meier curves will be used to estimate the survival distributions of overall survival and progression-free survival for each cohort. Each of these variables is measured from the date of study registration to the date of event (ie, death and/or disease progression) or the date of last follow-up if no event has occurred.
- Clinical benefit rate (CBR) at 6 months. The 6-month CBR will be calculated by the number of patients who have achieve a response and/or are progression-free and alive at 6 months divided by the total number of evaluable patients. Exact binomial 95% confidence intervals for CBR will be calculated.
- Correlative markers will be explored in this trial in relation to clinical outcomes of interest, and in particular in relation to the primary endpoint of overall response. Given the limited overall sample size as well as the relatively limited expected proportion of responses, these analyses will be largely exploratory and hypothesis-generating in nature. Correlative gene and protein markers will be summarized univariately in a quantitative manner and also summarized by clinical outcome group (e.g. response vs. no response). Graphical analyses will be largely used to assess potential patterns and relationships; e.g. side-by-side boxplots to assess differences in continuous marker levels between those with vs. without the clinical improvement (e.g. response vs. no response). Overall, hypothesis testing will largely be avoided given the sample size limitations but we will still obtain important preliminary data that can inform future studies and help better understand the mechanisms of this treatment regimen in this patient population.
- We would also evaluate and summarize the logistical aspects of the trial, including the rate of participation and enrollment of those screened and identified with the eligible genetic alterations. Also, of those enrolled, we will characterize the composition of the cohorts. Disease group-specific outcomes will also be summarized and described, although we will not be powered for any formal evaluation within a disease or histology subset. Still, these will be used as valuable preliminary data for hypothesis generation and designing future trials with this regimen and/or this treatment approach.

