5.4 Duration of Follow Up

Patients will be followed every 3 months for 52 weeks after removal from study or until death, whichever occurs first, in order to document time of progression (if patient did not progress while on study), survival, and to document subsequent alternate therapy received. Patients removed from study for unacceptable adverse event(s) will be followed until resolution or stabilization of the adverse event.

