10. STUDY CALENDAR

Baseline evaluation must be conducted within 2 weeks prior to start of ponatinib therapy. Imaging studies must be done \leq 4 weeks prior to the start of therapy. In the event that the patient's condition is deteriorating, laboratory evaluations should be repeated within 48 hours prior to initiation of the next cycle of therapy. Appropriate delays in study treatment or procedures are allowed to adjust for holidays or weekends. Each cycle is **28** days.

Study Assessment ^{s¹}	Screen	During Ponatinib Therapy		Final Study Visit ³	Follow-Up ⁹
Informed Consent	X				
Baseline Demographics	X				
Ophthalmic Exam ²	X	As clinically indicated			
Medical History / Interim History	X	Day 1 (\pm 3 days) of each cycle		X	
Concomitant Medications	X	Continuous			
Physical Exam	X	Day 1 (\pm 3 days) of each cycle		X	
ECOG Performance Status	X	Day 1 (\pm 3 days) of each cycle		X	
Vital Signs (BP, HR, Temperature, weight)	X	Day 1 (\pm 3 days) of each cycle		X	
Blood Pressure (at home) ⁴		Twice per week during cycle			
Chemistry ⁵	X	Day 1 (\pm 3 days) of each cycle		X	
Triglycerides	X				
CBC, Diff, Plt	X	Every 2 weeks for first 2 cycles	Day 1 (\pm 3 days) from cycle 3		
Liver Function Testing		Cycle 1 Day 1	Once per month, or more frequent if clinically indicated		
Serum Amylase, Serum Lipase	X	Every 2 weeks for first 2 cycles	Day 1 (\pm 3 days) from cycle 3		
Pregnancy Test ⁶	X				
12-Lead ECG	X	Repeated as Clinically Indicated			
LVEF (ECHO)	X	Repeated every 3 cycles \pm 7 days or as Clinically Indicated			
Research Biopsy(s) ⁷	Research biopsies on eligible	Research biopsies will be attempted on all patients at time of progression			

	patients prior to the study			
Study Agents		Ponatinib will be administered daily		
Tumor measurement S ⁸	X	Staging will occur after every 2 cycles \pm 7 days or as Clinically Indicated		
Adverse Events		Continuous		

1. Assessments scheduled on days of dosing must be done prior to administration of study drug(s), unless otherwise specified.
2. Ophthalmic exam will include indirect and direct fundoscopy, visual acuity, visual field examination, tonometry and color fundus photos. Additional ophthalmic exams will be performed if symptomatically warranted.
3. Final Study Visit must occur 21 days (\pm 7 days) after last dose of study drug.
4. Blood pressure cuff will be provided by Takeda. Patients will record readings in diary (Appendix B) and bring with them to clinic visits.

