11.1.4.3. Evaluation of Best Overall Response

The best overall response is the best response recorded from the start of the treatment until disease progression/recurrence (taking as reference for progressive disease the smallest measurements recorded since the treatment started). The patient's best response assignment will depend on the achievement of both measurement and confirmation criteria.

For Patients with Measurable Disease (*i.e.*, Target Disease)

Target Lesions	Non-Target Lesions	New Lesions	Overall Response	Best Overall Response when Confirmation is Required*
CR	CR	No	CR	≥ 4 wks. Confirmation**
CR	Non-CR/Non-PD	No	PR	
CR	Not evaluated	No	PR	
PR	Non-CR/Non-PD/not evaluated	No	PR	≥ 4 wks. Confirmation**
SD	Non-CR/Non-	No	SD	Documented at least once ≥ 4

	PD/not evaluated			wks. from baseline**
PD	Any	Yes or No	PD	no prior SD, PR or CR
Any	PD***	Yes or No	PD	
Any	Any	Yes	PD	

* See RECIST 1.1 manuscript for further details on what is evidence of a new lesion.
 ** Only for non-randomized trials with response as primary endpoint.
 *** In exceptional circumstances, unequivocal progression in non-target lesions may be accepted as disease progression.

Note: Patients with a global deterioration of health status requiring discontinuation of treatment without objective evidence of disease progression at that time should be reported as “*symptomatic deterioration*.” Every effort should be made to document the objective progression even after discontinuation of treatment.

For Patients with Non-Measurable Disease (i.e., Non-Target Disease)

Non-Target Lesions	New Lesions	Overall Response
CR	No	CR
Non-CR/non-PD	No	Non-CR/non-PD*
Not all evaluated	No	not evaluated
Unequivocal PD	Yes or No	PD
Any	Yes	PD

* ‘Non-CR/non-PD’ is preferred over ‘stable disease’ for non-target disease since SD is increasingly used as an endpoint for assessment of efficacy in some trials so to assign this category when no lesions can be measured is not advised

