11.1.6 Progression-Free Survival

PFS is defined as the duration of time from start of treatment to time of progression or death, whichever occurs first.

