12. STATISTICAL CONSIDERATIONS

12.1 Study Design/Endpoints

With the advent of genomic profiling and targeted therapies, focusing on patients with a specific target (or genomic alteration) of interest regardless of disease type or histology is a new paradigm that cancer research is beginning to adopt. This is a Phase-2, "basket" study for patients with advanced cancers (stage 4, any histology) who have disease progression with at least one prior regimen, identified with predefined genomic alterations. Two separate cohorts will be accrued in parallel, defined by genomic *FGFR*, as well as *KIT*, *PDGFR α* , *ABL1*, *RET*, and *FLT3* alterations.

Cohort A will consist of patients identified with activating mutations or fusions in *FGFR* as well as patients with *FGFR* amplifications.

Cohort B will consist of patients identified with rare gene targets (*KIT*, *PDGFR α* , *RET*, *ABL1*, and *FLT3* alterations) for whom there may be downstream targeting and efficacy associated with ponatinib.

Our goal is to assess efficacy outcomes in these two cohorts when treated with ponatinib.

(a) Definition of primary outcome/endpoint:

The primary endpoint for each of the cohort in this study is overall response. Overall response is defined as the number of patients who achieve any response in the first 6 cycles of treatment. All eligible patients, selected by a CLIA approved assay, who have received at least one dose of ponatinib will be evaluable for response. Response for tumors would be assessed using the RECIST 1.1 criteria (using CT scans or calipers by clinical exam) where response will be defined as a partial or complete response.

(b) Definition of secondary outcomes/endpoints:

- Toxicity is defined as adverse events that are classified as either possibly, probably, or definitely related to study treatment per NCI CTCAE v4.0
- Overall survival is defined as the time from treatment initiation to death.
- Progression-free survival defined as the time from treatment initiation to progression or death

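### Section 12.4 times PFS and OS from registration rather than first dose, and censors PFS at last follow-up although no scan is scheduled after treatment ends, so PFS can be biased upward.

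*Combined protocol and SAP*

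**What the plan says.** **Time origin.** Section 12.1(b) gives: "Progression-free survival defined as the time from treatment initiation to progression or death", and for the other endpoint: "Overall survival is defined as the time from treatment initiation to death". Section 11.1.6 agrees on PFS: "PFS is defined as the duration of time from start of treatment to time of progression or death". Section 12.4, which governs the Kaplan-Meier analysis, differs: "Each of these variables is measured from the date of study registration".

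**Censoring.** The same sentence of 12.4 closes both endpoints with a single rule: "ie, death and/or disease progression) or the date of last follow-up if no event has occurred". No separate rule for PFS refers to the last tumor assessment.

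**Assessment of progression.** The Study Calendar (Section 10) reads "Staging will occur after every 2 cycles", in the column for the period on ponatinib. The tumor-measurement row is empty for the final visit and for follow-up. Section 5.4 sets 3-monthly follow-up for 52 weeks, "in order to document time of progression (if patient did not progress while on study", but names no imaging. Calendar footnote 9 allows these contacts by telephone once toxicity has resolved. For patients who stop because of symptomatic deterioration, Section 11.1.4.3 adds: "Every effort should be made to document the objective progression even after discontinuation of treatment".

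**The concern.** Censoring at last contact suits OS, because any contact establishes that the patient is alive. It does not suit PFS, because a telephone call does not establish that a tumor has not grown. Under 12.4 a patient who stops for toxicity or withdraws stays in the PFS risk set, counted as progression-free, until progression is picked up, the patient dies or follow-up ends. This raises the tail of the curve and any landmark rate read from it. The 6-month clinical benefit rate in 12.4 also needs progression-free status at 6 months, so it shares the gap.

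PFS is a named secondary objective (Section 1.2). With a single arm, no control group carries the same error, so the bias goes straight into the reported estimate. Stopping without progression is foreseeable: Section 5.3 lists several such reasons, and in the GIST study summarized in Section 2.2.1 seven patients stopped for adverse events, mostly with onset in the first 2 weeks. The two time origins are a smaller matter, but they give two values for the same endpoint.

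**Working it through.** The plan states no PFS median, rate or event count, so there is no figure to reproduce.

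**Origin.** Section 4.1 asks for treatment to start within 5 business days of registration, about 7 calendar days. The registration origin adds at most about 7/30.4 = 0.23 month per patient if that window is kept.

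**Censoring: inputs.**
- From the documents: scans every 8 weeks on treatment (Sections 10 and 11.1), contacts every 3 months (taken as 13 weeks) for 52 weeks afterwards (5.4), and 30 patients (Cohort A).
- Assumed: exponential time to progression with median 8 or 16 weeks; 20% stop without progression, uniformly over weeks 1 to 8; exponential survival after progression with median 30 weeks; off-treatment progression captured with probability 0, 0.5 or 1.
- The 20% matches the GIST study: 19 patients are given as 54.3%, so n = 35, and 7/35 = 20%.

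**Hand check with no capture, median 8 weeks.** Follow-up lasts 52 weeks after stopping, so nobody is censored before week 26 and the Kaplan-Meier value is a simple proportion.
1. Reference with continued scanning: the last scan before week 26 is at week 24, so PFS = 2^(−24/8) = 0.125.
2. Patients who stop, at week 4.5 on average, count as failures only if they die within the remaining 21.5 weeks. With λ = ln2/8 = 0.0866 and μ = ln2/30 = 0.0231, P(alive) = (λe^(−21.5μ) − μe^(−21.5λ))/(λ − μ) = (0.0866×0.6085 − 0.0231×0.1552)/0.0635 ≈ 0.773.
3. With continued scanning, the patients who stop would have had 2^(−19.5/8) = 0.185. The rest therefore have (0.125 − 0.2×0.185)/0.8 = 0.110.
4. Rule in 12.4: 0.2×0.773 + 0.8×0.110 = 0.243, against 0.125.

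The same steps with a 16-week median give 0.2×0.854 + 0.8×0.335 = 0.438, against 2^(−24/16) = 0.354.

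**Simulation** (4,000 trials of 30 patients per setting; 26-week PFS with 20% stopping):

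| Median (weeks) | Capture | Continued scanning | Rule in 12.4 | Last-scan censoring |
|---|---|---|---|---|
| 8 | none | 0.124 | 0.243 | 0.176 |
| 8 | half | 0.124 | 0.196 | 0.161 |
| 8 | all | 0.124 | 0.148 | 0.146 |
| 16 | none | 0.353 | 0.438 | 0.372 |
| 16 | half | 0.354 | 0.409 | 0.369 |
| 16 | all | 0.352 | 0.377 | 0.364 |

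Bias under 12.4 with no capture: 0.243 − 0.124 = 0.119 and 0.438 − 0.353 = 0.085. With full capture: 0.024 and 0.025. Last-scan censoring leaves 0.012 to 0.052.

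**Sensitivity.**
- With 10% stopping and no capture: 0.184 against 0.124, and 0.395 against 0.354. With full capture: 0.137 against 0.125, and 0.366 against 0.355.
- Changing survival after progression to a median of 15 or 60 weeks (20% stopping, no capture) gives 0.211 or 0.262 at median 8 and 0.417 or 0.454 at median 16.
- Censoring deaths that occur more than 16 weeks after the last scan moves the last-scan result to 0.107 to 0.142 (median 8) and 0.331 to 0.360 (median 16), on either side of the reference.
- A separate simulation used other assumptions: median 4 months, stopping throughout treatment at a rate giving about 20%, and 15% of PFS events being deaths. With no capture, 6-month PFS was 42.8% under 12.4, 36.6% with last-assessment censoring and 35.4% in truth. Across medians of 3, 4 and 6 months and 10% to 40% stopping, 12.4 always gave the higher 6-month PFS.

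**The case against.** Follow-up exists partly to record progression, Section 11.1.4.3 asks for effort to document it, and Section 11.1 sets re-evaluation every 8 weeks without limiting it to patients on drug. On that reading, last follow-up could mean the last contact at which progression was assessed, and zero capture is a worst case. This narrows the likely bias, but 12.4 does not say so. The calendar places staging under therapy, and a stated aim is not a scheduled scan.

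The modelled size can also be challenged, and these points stand:
- The residual with full capture comes mostly from 13-weekly contacts. With 8-weekly contacts it falls to 0.131 against 0.125 and 0.358 against 0.351.
- The model has no scan at stopping, although the calendar permits clinically indicated staging. Adding one lowers the no-capture figures from 0.242 to 0.208 and from 0.444 to 0.422.
- The larger leukemia study in Section 2.2.1 gives 68/449 = 15% stopping for adverse events rather than 20%.
- Last-scan censoring is itself informative when early stoppers are censored at day 1 while those who die count as events.
- PFS carries no decision rule. With 30 patients the approximate 95% half-width is 12 points at 12% and 17 points at 35%, at least as large as the worst modelled bias.

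These points limit the weight of the finding. They do not supply the missing PFS rule, and sampling error does not excuse an error with a known direction.

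**Conclusion.** The concern holds. The origin contradiction is plain on the text and small, about a week at most if the window is kept. The censoring rule, followed as written, biases PFS upward. Under the assumptions above with 20% stopping early, 26-week PFS is overstated by about 2 points if all off-treatment progression is captured and by 8 to 12 points if none is; with 10% stopping, by about 1 and 4 to 6 points. The direction was the same in every setting examined. The size is illustrative, because the stopping share, the capture rate and survival after progression are not in the documents. The response-rate decision rule and OS censoring are not affected.

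**What to change.** In Section 12.4:
- Time PFS and OS from first dose, as 11.1.6 and 12.1 already do.
- For patients without documented progression or death, censor PFS at the last adequate tumor assessment, or at day 1 if there is none. Keep last-contact censoring for OS only.
- State how a death after a long unscanned gap is counted, since that choice moves the estimate to either side of the reference. State also how the start of new anticancer therapy is handled, since 5.4 collects it.
- Report the last-follow-up version as a sensitivity analysis, and say that without scheduled off-treatment imaging some bias remains (1 to 5 points in the main simulation).

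The cost is a few sentences and no new procedures. In the main simulation, 26-week PFS would be 0 to 7 points lower than under the present rule, and patients who stop before any post-baseline scan would contribute little information.

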12.5 Reporting and Exclusions

12.5.1 Evaluation of Toxicity

All patients would be evaluable for toxicity from the time of their first treatment with ponatinib.

12.5.2 Evaluation of Response

All patients included in the study must be assessed for response to treatment, even if there are major protocol treatment deviations or if they are ineligible. Each patient will be assigned one of the following categories: 1) complete response, 2) partial response, 3)

stable disease, 4) progressive disease, 5) early death from malignant disease, 6) early death from toxicity, 7) early death because of other cause, or 9) unknown (not assessable, insufficient data). [Note: By arbitrary convention, category 9 usually designates the "unknown" status of any type of data in a clinical database.]

All of the patients who met the eligibility criteria (with the possible exception of those who received no study medication) should be included in the main analysis of the response rate. Patients in response categories 4-9 should be considered to have a treatment failure (disease progression). Thus, an incorrect treatment schedule or drug administration does not result in exclusion from the analysis of the response rate. All conclusions should be based on all eligible patients. Subanalyses may then be performed on the basis of a subset of patients, excluding those for whom major protocol deviations have been identified (*e.g.*, early death due to other reasons, early discontinuation of treatment, major protocol violations, etc.).

APPENDIX A PERFORMANCE STATUS CRITERIA

ECOG Performance Status Scale		Karnofsky Performance Scale	
Grade	Descriptions	Percent	Description
0	Normal activity. Fully active, able to carry on all pre-disease performance without restriction.	100	Normal, no complaints, no evidence of disease.
		90	Able to carry on normal activity; minor signs or symptoms of disease.
1	Symptoms, but ambulatory. Restricted in physically strenuous activity, but ambulatory and able to carry out work of a light or sedentary nature (e.g., light housework, office work).	80	Normal activity with effort; some signs or symptoms of disease.
		70	Cares for self, unable to carry on normal activity or to do active work.
2	In bed <50% of the time. Ambulatory and capable of all self-care, but unable to carry out any work activities. Up and about more than 50% of waking hours.	60	Requires occasional assistance, but is able to care for most of his/her needs.
		50	Requires considerable assistance and frequent medical care.
3	In bed >50% of the time. Capable of only limited self-care, confined to bed or chair more than 50% of waking hours.	40	Disabled, requires special care and assistance.
		30	Severely disabled, hospitalization indicated. Death not imminent.
4	100% bedridden. Completely disabled. Cannot carry on any self-care. Totally confined to bed or chair.	20	Very sick, hospitalization indicated. Death not imminent.
		10	Moribund, fatal processes progressing rapidly.
5	Dead.	0	Dead.

